STUDY PROTOCOL (last updated: 15 March 2020)

Study Title: Silver Diamine Fluoride and Papain-Based Gel for Management of MIH-affected Molar in Paediatric Patients

Study Summary:

This randomised controlled trial of MIH affected first permanent molar requiring interim restorative treatment (ITR) aim to determine the clinical outcome of additional usage of Silver Diamine Fluoride (SDF) with and without papain-based gel on MIH molars at 12 months duration. SDF and Papain-based gel are the additional to the conventional Glass Ionomer Cement ITR.

Study Description:

Rationale

Molar Incisor Hypomineralization (MIH) is a systemic origin, qualitative developmental defect of enamel affecting one to four first permanent molars and frequently involving incisors (Weerheijm, 2001). Lesion presented as well-demarcated discolouration of the enamel, or enamel destruction due to breakdown or dental caries with a global prevalence was estimated around 14.2% (Schwendicke F et al, 2018). MIH teeth presented with various clinical problem including increase susceptibility of caries and post eruptive breakdown, inferior bonding to composite restoration, recurrent restorative failure, hypersensitivity, and difficulty to achieve anaesthesia. Extraction of the MIH affected first permanent molar is an option and require comprehensive evaluation and 'ideal' time. Currently, acceptance to invasive restorative treatment and extraction is a significant challenge in children. Hence, a less-invasive treatment using glass ionomer cement (GIC) with remineralisation and desensitising agents that comply with principle of Minimal Intervention Dentistry (MID) has gained attention as interim therapeutic restoration in moderate to severe MIH affected tooth to prevent progression of disease. Silver Diamine is a high concentration topical fluoride agent has shown superior performance for remineralization and caries arrest (Gao et al., 2016). Papain based gel is a chemomechanical caries removal and deproteinizing agent assist to remove debris and protein without the need of rotary instrument(Deng et a., 2018). There is a paucity in the published literature regarding the effect of SDF and papain-based gel on MIH-affected teeth. To date, no study has been done to evaluate the clinical outcome of MIH-affected molars treated with papain-based gel as deproteinising agent and SDF followed by interim therapeutic restoration with GIC. It is hoped that findings obtained from this study will give new insight into managing MIH-affected molars in children

Objective:

The aim of the study is to determine the clinical outcome of additional SDF with and without papain-based gel on MIH molars versus HVGIC alone as interim therapeutic restoration at 6 and 12 months. Specifically, the objective of this study is

1. To determine and compare the clinical outcome determine as success and failure of treatment related to pulpal health, structural integrity and hypersensitivity on MIH molars treated with GIC alone or with or without the use of SDF and papain-based gel at 6 and 12 months

Methodology:

Study Design: This study is a single centre, three arms, parallel randomised controlled trial (RCT) on MIH molars in children aged 5 to 15-year-old presented with at least one molar tooth diagnosed as MIH. RCT was opted as it allows comparison of data with the conventional management using GIC which is a common interim therapeutic restorative material of choice.

Research Subject and Participant: MIH screening and diagnosis of the first permanent molar will be done using the European Academy of Paediatric Dentist (EAPD) MIH index by Ghanim et al., 2015, ICDAS caries assessment, clinical assessment, and radiographic evaluation. The inclusion criteria of the participant and molar include.

1. Children aged 5 – 15 years old
2. Healthy with no medical problem
3. Subject presented with at least one MIH FPM with:
 - a. Post eruptive breakdown (PEB)
 - b. Unsatisfactory atypical restoration
 - c. Atypical caries without pulp involvement

The exclusion criteria of the participant and molars include

1. Children with difficulty comprehending instruction
2. Children with inability to perform oral hygiene care independently
3. Known allergy to silver
4. Affected FPM with
 - a. Non MIH defect (Fluorosis, Amelogenesis Imperfecta)
 - b. No PEB and carious lesion
 - c. Lesion into the pulp

- d. Intact restoration
- e. Extensive coronal breakdown requiring extraction

Upon obtained of informed consent, based on the tooth as the unit, it will then be randomised (1:1:1 via blocks) to either intervention arms by an independent collaborator based on the allocation sequence. The collaborator will not be involved in the study and was responsible for keeping the randomisation list. The randomisation allocation sequence will be generated using computer software.

Intervention: Intervention will be carried out by single investigator who is not involved in assignment of the samples. Group 1 will receive High Viscous Glass Ionomer Cement (HVGIC) restoration; Group 2 will be treated with 38% SDF (RivaStar®) and restored with HVGIC, and Group 3 will receive papain-based gel, Papacarie Duo™ followed by 38% SDF application and HVGIC restoration. In this study, 38% SDF by the RivaStar was the only SDF available and marketed in Malaysia. It is approved by the Malaysia Device Authority and U.S Food and Drug Administration (FDA) in 2014. In addition, the papain base gel (Papacarie Duo™) was obtained from the manufacturer and has been used in many clinical studies as chemomechanical caries removal agent as well as deproteinizing agent to improve adhesion of composite (Goyal et al., 2015, Pithon et al., 2016, Bottega et al. 2018)

Observation: At 6- and 12-months follow-ups, the findings for this study will be assessed by a blinded assessor who was not involved in recruitment and intervention. The clinical parameters recorded include presence of pain, swelling, tenderness, abscess, enamel breakdown, restoration quality, presence of caries associated with the tooth and Schiff Cold Air Sensitivity Scale (SCASS). This clinical outcome of the molar; success or failure will then be determined based on the clinical parameters.

Table 1: Description of the clinical outcome

Outcome	Description
Success	
 • Absence of pain related to the treated tooth • Absence of tenderness to percussion • No evidence of swelling or presence of a sinus tract • Absence of enamel breakdown and caries along margin of restoration • No hypersensitivity (SCASS 0 or 1)
Major failure	
 • Presence of spontaneous throbbing or persistent pain • Presence of tenderness to percussion • Evidence of swelling and sinus
Minor failure	
 • Presence of new carious lesion or enamel breakdown at the margin of restoration • Presence of hypersensitivity (SCASS 2 or 3)

Sample size: The sample size is calculated based on Grossi et al., who reported that the clinical success of GIC (Equia Forte) restoration using ART technique in MIH affected permanent molars was 98.3% (Grossi et al., 2018). Since there was no literature reporting on the clinical success of Silver Diamine Fluoride and papain-based gel on MIH-affected molars, the success rate was assumed to be 50%. With an estimated error of 5% and power of 90%, the minimum estimated sample size was calculated to be 14 teeth per intervention group. The sample size calculation will be performed using G-power 3.1 software that calculated the power and sample size for tests by comparing two independent binomial populations with probabilities π_1 and π_2 , respectively. Pearson chi-square test was used to test the association of two binary variables (two groups and two outcomes). An additional 50% was added to compensate for the possibility of high dropout or recall failure. Hence, the number was increased to 21 teeth per group for a total of 63 teeth. The high percentage of dropout rate in this study is decided to accommodate a high need of retreatment of GIC restoration based on few published literature (Al Muallem et al., 2018; Linner et al., 2020). Besides, the high dropout rate may also be related to the higher chance of the affected molar to be extracted following advice by an orthodontist during the review phase.

Data Management and Analysis:

Data obtained will be entered and analysed using Statistical Package for the Social Sciences (SPSS) version 26.0 software. The continuous data will be checked for normality of distribution and reported accordingly. Categorical data in this study are the clinical parameters, clinical outcome, and restorative quality. Descriptive statistics of frequencies and percentages will be presented for categorical data. The primary data analysis will be done using Intention-to-treat (ITT) analysis involving all the samples recruited and randomised. The Per Protocol (PP) analysis will be done to compare the difference between treatment effects as a sensitive analysis of missing value. Comparison of categorical outcomes will be assessed using Chi-square goodness of fit test and Friedman Two-way Analysis of Variance (ANOVA) by Ranks test. Association studies such as factors affecting the outcome will be further evaluated using the Binary Logistic Regression. In all analyses, the level of significance is set at $p<0.05$. The power of the study will be calculated using G*Power Version 3.1.9.4 using the Post Hoc test of Goodness-of-Fit.

Ethical Consideration:

This study has already received approval from the Medical Ethics Committees, Faculty of Dentistry, University of Malaya (CD1912/0061/20155(P)). Patient Information Sheet (PIS) will be disseminated to parents and participated children before consenting. Written informed and verbal consent from parents and, where appropriate, the children, were obtained before intervention. Participation is based on a voluntary basis and they may decide to leave at any time of the study.

Reference:

1. Almualllem, Z. & Busutil-Naudi, A. 2018. Molar incisor hypomineralisation (MIH) – an overview. *British Dental Journal*, 225, 601-609.
4. Gao, S. S., Zhang, S., Mei, M. L., Lo, E. C.-M. & Chu, C.-H. 2016. Caries remineralisation and arresting effect in children by professionally applied fluoride treatment – a systematic review. *BMC Oral Health*, 16.

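### No method named in the plan compares the three arms on the ordered SCASS score (0-3), so a hypersensitivity comparison made with the named categorical methods would ignore the order of the levels

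*Combined protocol and SAP*

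**What the plan says.** The single specific objective is to compare "success and failure of treatment related to pulpal health, structural integrity and hypersensitivity on MIH molars" between treatments at 6 and 12 months (Objective).

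Under Observation, a blinded assessor records the clinical parameters at both visits. They include "presence of caries associated with the tooth and Schiff Cold Air Sensitivity Scale (SCASS"). Table 1 then uses the score in one way only: "No hypersensitivity (SCASS 0 or 1") belongs to success and "Presence of hypersensitivity (SCASS 2 or 3") to minor failure.

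The Data Management and Analysis section states: "Categorical data in this study are the clinical parameters, clinical outcome, and restorative quality". These are summarised as frequencies and percentages. On testing it says: "Comparison of categorical outcomes will be assessed using Chi-square goodness of fit test and Friedman Two-way Analysis of Variance (ANOVA) by Ranks test". It adds that "factors affecting the outcome will be further evaluated using the Binary Logistic Regression". It names no rank test for independent groups, no trend test and no ordinal regression.

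The Sample size section works on binary success, 98.3% for GIC against an assumed 50%. It arrives at 14 teeth per group, raised to 21. It gives no SCASS distribution, SCASS effect or separate SCASS sample size.

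**The concern.** Hypersensitivity is one of three domains in the objective, and the rationale presents desensitising agents as part of the treatment approach. A reader will expect the report to say whether the arms differ in hypersensitivity. The score that answers this has four ordered levels, but the named methods would treat it as two classes or as unordered categories.

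With the cut, a tooth that would score 1 under one treatment and 0 under another contributes nothing, and neither does a 3 against a 2. With unordered categories, a shift along the scale is spread over extra degrees of freedom. With as few as 14 evaluable teeth per arm, either choice makes a real shift easier to miss, and a non-significant result could then be reported as no desensitising effect.

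**Working it through.** **1. The plan's own figure.** For 98.3% v 50% at 5% and 90% power, the usual two-sided normal formula without continuity correction gives 16 per group, and the arcsine formula gives 12.3, rounded up to 13. Exact power of the two-sided Pearson test is 0.901 at 13 and 0.927 at 14. The stated 14 is in line with these, and 14 × 1.5 = 21. This figure belongs to the composite and says nothing about SCASS.

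**2. Which named methods use order between arms?**
- Chi-square: treats levels as unordered. The goodness-of-fit form does not itself compare arms, which is a separate matter. Pearson tests of independence stand in for it below.
- Friedman: uses ranks, but for related samples such as one tooth over visits. The arms are parallel.
- Binary logistic regression: needs the score cut in two.

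None compares parallel arms on the ordered score.

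**3. Information kept by the cut at 2.** Under proportional odds and small effects, with p_i the share of teeth at level i and q = P(SCASS ≥ 2):

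efficiency = 3q(1 − q) / (1 − Σp_i³)

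The distributions (levels 0/1/2/3, %) are assumptions.

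| Distribution | 3q(1−q) | 1−Σp³ | Kept | Lost |
|---|---|---|---|---|
| 5/45/45/5 | 0.750 | 0.818 | 0.92 | 8% |
| 25/25/25/25 | 0.750 | 0.938 | 0.80 | 20% |
| 30/30/25/15 | 0.720 | 0.927 | 0.78 | 22% |
| 50/25/15/10 | 0.563 | 0.855 | 0.66 | 34% |
| 70/20/7/3 | 0.270 | 0.649 | 0.42 | 58% |

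For the three middle rows, a 20-34% loss is worth 0.20 × 21 ≈ 4 to 0.34 × 21 ≈ 7 teeth per arm.

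**4. Limit implied by the sizing assumption.** Success requires SCASS 0 or 1. If 98.3% of HVGIC teeth succeed, at most 1.7% can score 2 or 3, so q = 0.017 and 3q(1 − q) = 0.050. The result depends on how the rest split between levels 0 and 1:
- 60% at level 0: 0.050 / 0.728 = 0.07 kept, 93% lost.
- 80% at level 0: 0.050 / 0.482 = 0.10 kept, 90% lost.
- 90% at level 0: 0.050 / 0.270 = 0.19 kept, 81% lost.

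The expected number of HVGIC teeth at level 2 or 3 is then 21 × 0.017 ≈ 0.4, so the cut has almost nothing to work with if the other arms score lower still.

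**5. Information lost by an unordered test.** This is the ratio of noncentralities needed for equal power at 5%:
- Two arms, 1 v 3 df: 7.85/10.90 at 80% power (28% lost); 10.51/14.17 at 90% (26%).
- Three arms, 2 v 6 df: 9.63/13.62 at 80% (29%); 12.65/17.42 at 90% (27%).

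**6. Simulated three-arm power.** Assumed odds ratios are 1/3/5 towards lower scores, with independent teeth. Entries are for HVGIC at 25/25/25/25, 30/30/25/15 and 50/25/15/10.

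| Test | 21 per arm | 14 per arm |
|---|---|---|
| Kruskal-Wallis, levels 0-3 | 72 / 69 / 60% | 51 / 50 / 41% |
| Cut at 2 (3×2 Pearson) | 59 / 52 / 35% | 42 / 34 / 20% |
| Unordered (3×4 Pearson) | 52 / 48 / 38% | 32 / 30 / 22% |

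Type I error was 4.1-5.7%. Repeat runs agreed within about 2 points. Under the limit in step 4, the ordered test has only about 7-34% power at 14 per arm and 12-51% at 21, and leads the unordered test by only about 3-6 points.

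**The case against.** The strongest reply is that the plan never promises a test of SCASS. The score is one input to a binary outcome, and the trial is sized on that outcome. This stands in part. A SCASS comparison can be inferred, because the clinical parameters are classed as categorical and categorical outcomes are to be compared, but it is not stated. If none was intended, the proposal adds p-values.

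A reader might infer that the plan makes no use of order anywhere. The documents do not support that, since Friedman is a rank test. It would suit a within-tooth comparison over visits, but it does not serve the arm comparison.

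A reader might also fix on a loss of 20-35% as the trial's own figure. It is not. It follows from a fairly even assumed spread of scores under proportional odds, and other assumed spreads give much less or much more.

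Two further limits stand. Teeth are randomised singly and a child may contribute more than one, so a plain rank test would treat related teeth as independent. And if a treatment moved teeth only across the boundary between 1 and 2, the ordered method would lose its advantage over the cut.

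**Conclusion.** The point holds as a gap in the SCASS analysis. The arms can be compared on hypersensitivity only by discarding the order of a score that is already collected. It does not show a loss of power for the success/failure composite, and it does not show that the cut in Table 1 is wrong. A reader might infer either, but the documents support neither.

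The size rests on assumptions. Under proportional odds the cut loses about 8-58% over the range of distributions tried, and 20-34% for the three used in the power table. It loses about 81-93% at the limit set by 98.3% HVGIC success, and exceeds 90% there only if a sizeable share of teeth score 1. That limit takes the cited success rate to share Table 1's definition, which the documents do not say, and it describes the HVGIC arm only.

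An unordered test loses about 26-29% under moderate spread, but only a few points of power at that limit. No method makes the comparison strong at 14-21 teeth per arm.

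**What to change.** Leave Table 1 and the composite unchanged. In Data Management and Analysis, state that SCASS 0-3 is compared between the three arms at 6 and 12 months as a secondary analysis with a method that uses the order. A proportional-odds model with arm is preferable, with child-clustered standard errors or a child random effect, reported as odds ratios with 95% confidence intervals. Kruskal-Wallis would do only if each child contributes one tooth. Show the percentage with SCASS 0-1 per arm descriptively. Say that Friedman, if kept, addresses change over visits and not the arm comparison.

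The cost is a few sentences, with no new data, visits or teeth. There are three downsides:
- The tested effect is a shift in score and not a percentage, so the percentage must appear beside it.
- One secondary p-value per visit is added if no SCASS comparison was intended.
- Power stays modest, so the plan should say that a null result will not be read as no effect.

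### The 90% power holds for one scenario only (GIC 98.3% vs add-on 50%), and the analysis plan names no between-arm difference or confidence interval to show what a non-significant arm comparison leaves open

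*Combined protocol and SAP*

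**What the plan says.** The Sample size section takes 98.3% success for GIC from a published study. For SDF and papain-based gel it found no literature, so "the success rate was assumed to be 50" per cent. This is one value, not separate values for Groups 2 and 3. The test is a two-group one: "Pearson chi-square test was used to test the association of two binary variables (two groups and two outcomes"). The result is: "With an estimated error of 5% and power of 90%, the minimum estimated sample size was calculated to be 14 teeth per intervention group". The number was then raised to 21 per group, 63 in total: "An additional 50% was added to compensate for the possibility of high dropout or recall failure".

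The Objective section sets the aim as "to determine the clinical outcome of additional SDF with and without papain-based gel on MIH molars versus HVGIC alone", and the numbered objective is "To determine and compare the clinical outcome determine as success and failure of treatment" across the treatments. Neither gives a direction.

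On reporting, the Data Management and Analysis section says "Descriptive statistics of frequencies and percentages will be presented for categorical data". Categorical outcomes are to be compared with a chi-square goodness-of-fit test and the Friedman test. Binary logistic regression is reserved for factors affecting the outcome. "In all analyses, the level of significance is set at" p<0.05. A post hoc power calculation is planned for a goodness-of-fit test. No effect measure and no confidence interval is named for any pair of arms.

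**The concern.** The trial has three arms and a comparative objective, but its power statement rests on a single contrast in which the add-on does 48.3 points worse than GIC (98.3 − 50). Two answers that the objective invites fall outside it: whether papain-based gel adds anything to SDF (Group 3 vs Group 2), and whether an add-on improves on GIC when GIC already does as well as assumed.

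Low power for some contrasts is common in a small three-arm trial and can be tolerated if the results are reported with their uncertainty. Here the analysis plan does not provide for that. Goodness of fit sets counts against expected proportions, and Friedman is for related measurements, so neither estimates a difference between independent arms. Followed as written, the plan yields percentages and p-values. A reader who sees a non-significant Group 3 vs Group 2 result beside a stated 90% power has nothing in the planned output to show that a large difference remains possible.

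**Working it through.** **Inputs.** From Sample size: success 98.3% (GIC) and 50% (add-on), error 5%, Pearson chi-square, 14 per group, 21 after the allowance for loss. Assumptions of this review: two-sided test (the plan does not state sidedness), independent teeth, no multiplicity adjustment, and 70% as an illustrative Group 3 rate.

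**1. The plan's own figure.**
- Unpooled normal approximation: n = (1.960 + 1.282)² × (0.983×0.017 + 0.5×0.5) / 0.483² = 10.51 × 0.2667 / 0.2333 = 12.01, so 13 per group.
- Pooled approximation: 16 per group.
- Exact power at n = 14 is the sum, over GIC results, of P(GIC result) × P(add-on result low enough for p<0.05):

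| GIC successes | Probability at 98.3% | Add-on successes needed | Probability at 50% | Product |
|---|---|---|---|---|
| 14 | 0.7866 | ≤10 | 0.9713 | 0.7640 |
| 13 | 0.1904 | ≤8 | 0.7880 | 0.1501 |
| 12 | 0.0214 | ≤7 | 0.6047 | 0.0129 |
| 11 | 0.0015 | ≤5 | 0.2120 | 0.0003 |

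The total is 0.927. The stated 14 lies between the two approximations and gives at least 90% power by exact calculation.

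**2. Benefit over GIC at the assumed 98.3%.** The ceiling is 100 − 98.3 = 1.7 points. If every add-on tooth succeeds, Pearson reaches p<0.05 only when GIC has at least 4 failures:
- 14/14 vs 10/14: chi-square = 28×(14×4)²/(14×14×24×4) = 4.67, p = 0.03.
- 14/14 vs 11/14: chi-square = 28×(14×3)²/(14×14×25×3) = 3.36, p = 0.07.
- P(at least 4 failures of 14, each with probability 0.017) = 0.00007, that is 0.01%.
- With 21 per group, at least 4 failures are again needed: 0.0004, that is 0.04%.

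**3. Group 3 vs Group 2.** No difference is planned, so one must be assumed. For 50% vs 70%, the same exact enumeration gives 17.7% power at 14 per group and 26.1% if all 21 outcomes are observed.

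**4. What an interval would show.** Newcombe 95% interval for a difference, built from the Wilson limits (l, u) of each arm: lower = d − √[(p₁−l₁)² + (u₂−p₂)²], upper = d + √[(u₁−p₁)² + (p₂−l₂)²].
- 10/14 vs 7/14: Wilson limits 0.454 to 0.883 and 0.268 to 0.732; d = +21.4 points, interval −13.5 to +50.1; Pearson chi-square 1.35, p = 0.25.
- 7/14 vs 7/14: d = 0, interval −32.8 to +32.8.
- 14/14 vs 14/14: d = 0, interval −21.5 to +21.5; a Wald interval has zero width.

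The last case matters only if both arms do very well. Its probability is 0.983²⁸ = 0.62 if both are at 98.3%, but about 0.005% (0.787 × 0.5¹⁴) under the plan's 98.3% vs 50%.

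**The case against.** The strongest reply is that the power sentence already shows its scope: it follows both assumed rates and is followed by the description of a two-group test. The 50% is openly a placeholder, and the headline aim is add-on versus HVGIC, so Group 3 vs Group 2 may be secondary. Much of this stands, which is why the power sentence needs only clarification. It does not supply the missing effect estimate.

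A reader might infer that the trial has no power for any benefit over GIC. The documents do not support that. The two-sided test is symmetric: GIC 50% vs add-on 98.3% has the same 92.7% power at 14 per group. The 98.3% is a planning input, and the same section expects a high need for GIC retreatment. The limit holds only if GIC success is near 98.3%. For an intermediate case, GIC 70% vs add-on 90% (both assumed), power is 25% at 14 and 38% at 21 per group.

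It can also be said that logistic regression could produce an interval, and that the per-protocol analysis mentions treatment effects. Neither defines an arm contrast, an effect measure or an interval. Nor do the documents say that a non-significant result will be read as no effect; that is a risk of the reporting, not a stated intention.

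Finally, a plain Newcombe interval assumes independent teeth, whereas the Methodology section randomises by tooth and admits children with one or more affected molars. This stands, and the fix allows for it.

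**Conclusion.** The concern holds in a limited form. The 14 teeth and the 90% are right for 98.3% vs 50%; nothing here shows a sample size error. The figure does not carry over to Group 3 vs Group 2 (about 18% power at 14 and 26% at 21 per group for 50% vs an assumed 70%), nor to a benefit over GIC if GIC success is near 98.3% (0.01% and 0.04%). The part that matters most is in the analysis plan: no between-arm difference or interval is pre-specified, although with 14 teeth per group even equal observed success of 7/14 leaves about 33 points open in either direction.

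All figures take the test as two-sided and the teeth as independent, and ignore multiplicity.

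One might go further and count lost teeth as failures, which would cut power in the plan's own scenario to about 55% if one third of 21 were lost. The documents state no such imputation rule, so that figure carries no weight here.

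**What to change.** **Data Management and Analysis (main change).** Add: *Success at 6 and 12 months will be compared between arms (Group 2 vs 1, 3 vs 1, 3 vs 2) as a risk difference with 95% CI, using a score-based method such as Newcombe if each child contributes one tooth, or a version that allows for clustering if children contribute more than one. A non-significant result will not be read as no effect.*

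**Sample size (scope of the stated figure).** Add: *The 90% power applies to a two-group comparison of 98.3% vs 50% success with 14 evaluable independent teeth per group. No difference between Groups 2 and 3 was assumed, and if GIC success is near 98.3% the trial cannot show a benefit over GIC.*

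The cost is four sentences, with enrolment and treatment unchanged. The power statement will look less favourable and the intervals will be wide. The change gives six intervals (three pairs, two visits). It does not settle multiplicity or the suitability of the goodness-of-fit and Friedman tests, which need their own attention.

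### Table 1 has no failure item for a study restoration repaired or replaced between visits, so retreatment that the plan expects is never counted as a failure

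*Combined protocol and SAP*

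**What the plan says.** The Objective sets out to compare "success and failure of treatment related to pulpal health, structural integrity and hypersensitivity on MIH molars", so the state of the restored tooth is meant to be part of the outcome.

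The Observation paragraph lists what the blinded assessor records at 6 and 12 months: "The clinical parameters recorded include presence of pain, swelling, tenderness, abscess, enamel breakdown, restoration quality, presence of caries associated with the tooth", together with the cold-air sensitivity score (SCASS). It then says: "This clinical outcome of the molar; success or failure will then be determined based on the clinical parameters".

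Table 1 makes that determination. On structure, the Success row asks for "Absence of enamel breakdown and caries along margin of restoration", and the Minor failure row lists "Presence of new carious lesion or enamel breakdown at the margin of restoration". The other items concern pain, percussion tenderness, swelling or sinus, and hypersensitivity. No row mentions repair or replacement of the restoration, and no row uses restoration quality.

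The Sample size section explains the enlargement from 14 to 21 teeth per group: "An additional 50% was added to compensate for the possibility of high dropout or recall failure". It adds "The high percentage of dropout rate in this study is decided to accommodate a high need of retreatment of GIC restoration", and also cites extraction on orthodontic advice.

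Data Management and Analysis makes intention-to-treat on all randomised teeth primary, with per-protocol as a sensitivity analysis. It lists restorative quality as a categorical variable separate from clinical outcome. It gives no value for a retreated tooth.

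**The concern.** The plan anticipates that study restorations will need to be redone, but the event appears only in the reasoning about dropout and never as an outcome. Table 1 reads the tooth at the visit. A repair or replacement between visits can remove the signs that Table 1 would have caught before the assessor sees the tooth.

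If retreated teeth are scored on what is found, success can be overstated in any arm, since all three arms receive HVGIC. If retreatment is more common in one arm, the comparison is biased, and the documents do not tell us in which direction. With no rule stated in advance, the scoring could also be settled after results are known.

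**Working it through.** **1. The plan's own figure.** Inputs from the Sample size section: success 98.3% (GIC) and 50% (assumed for the new treatments), 5% error, 90% power. The sidedness is not stated. The pooled two-proportion formula is

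n = [z(1−α/2)·√(2p̄(1−p̄)) + z(0.90)·√(p1(1−p1) + p2(1−p2))]² / (p1−p2)², with p̄ = (0.983 + 0.5)/2 = 0.7415.

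Two-sided: (1.960 × 0.619 + 1.282 × 0.516)² / 0.483² = 15.1, so 16 per group. The one-sided version gives 13. Exact enumeration of the two-sided Pearson chi-square test gives 92.7% power at 14 per group. The stated 14 is therefore reasonable, and 14 × 1.5 = 21 and 21 × 3 = 63 follow.

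**2. Table 1 applied to a retreated tooth.** Take a tooth re-restored at month 8 and sound at month 12. It has no pain, no tenderness, no swelling or sinus, no marginal caries or enamel breakdown, and a SCASS of 0 or 1. All five Success items are met and no failure item is. The same holds for a tooth re-restored before month 6 and sound at that visit. If the tooth is instead taken as a dropout, it has no outcome at all. Neither route leads to failure.

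**3. Effect on the success rate.** Scoring one tooth as Success instead of failure changes a 21-tooth arm by 1/21 = 4.8 points. The difference between two arms shifts by (k_control − k_comparison)/21:
- 3 versus 1: +9.5 points
- 1 versus 3: −9.5 points
- equal numbers: 0

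If k control teeth are left out rather than failed, the expected control rate stays at 98.3% instead of (21 − k) × 0.983/21. That is 93.6% for k = 1, 84.3% for 3 and 74.9% for 5.

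**4. Effect on power.** Exactly k teeth in each arm are retreated. The other 21 − k succeed with probability 0.983 or 0.5. The test is the two-sided 5% Pearson chi-square without continuity correction on all 21 per arm, with every outcome enumerated. At k = 0 power is 99.1%.

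| k per arm | Retreated = failure | Retreated = Success |
|---|---|---|
| 1 | 97.5% | 98.8% |
| 2 | 94.9% | 98.3% |
| 3 | 92.2% | 97.7% |
| 5 | 72.5% | 95.7% |
| 7 | 55.6% | 92.3% |

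The values of k are illustrations, because the documents give no retreatment rate. The table assumes that 98.3% and 50% do not already count retreatment, which the documents do not say.

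**The case against.** The best defence is that the sample size section places retreatment within dropout, so the authors may mean retreated teeth to leave assessment rather than be re-scored as Success. That is a fair reading of intent. But the sentence justifies a sample size and excludes no tooth. Nor does intention-to-treat resolve the matter: it fixes which teeth are analysed, not what value a retreated tooth takes. If the teeth are missing, the expected failure still goes uncounted.

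A second defence is that tooth status at a visit is a legitimate target for an interim restoration, and that the plan handles part of the problem already. Restoration quality is recorded and reported separately, and a Table 1 failure present at month 6 is counted at that visit. This stands in part. Teeth with marginal caries, enamel breakdown, hypersensitivity or pulpal signs at a visit are failures already and lie outside this point. However, the plan does not say that it chose visit status, its objective speaks of success and failure of treatment, and a replaced restoration may score well on quality.

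Three stronger readings are tempting and are not supported:
- A reader might infer that a lost restoration would also be scored as Success. Table 1 presupposes a restoration with a margin, and loss may re-expose the defect for which the tooth was enrolled, so this is not plain from the text.
- A reader might take 21 − 14 = 7 as the most teeth per arm that could be retreated. It is an allowance for losses of all kinds and caps nothing.
- A reader might conclude that power falls below 90% at three retreated teeth per arm. Treating k/21 as a probability for every tooth, so that k is only an expected count, gives 83.6%. With exactly three retreated teeth it is 92.2%.

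**Conclusion.** The point holds. As written, the outcome definition lets a repaired or replaced study restoration count as Success or, on the dropout reading, as missing, but never as failure. This is more than missing detail, because Table 1 applied by its letter gives an answer at odds with an objective that covers structural integrity.

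The omission rests on the text alone and needs no assumption. Its size is unknown. Each affected tooth is worth 4.8 points in its arm. The bias in the comparison is zero if retreatment is equal across arms and can go either way if it is not. With up to three retreated teeth per arm scored as failure, power stays above the planned 90%; at five it is well below. These power figures depend on the planning rates not already counting retreatment. It should be fixed before analysis. Confidence is medium, because neither the retreatment rate nor the authors' intent is stated.

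**What to change.** Before analysis, reconcile the Observation section with Table 1, the Sample size section, and Data Management and Analysis:

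1. Add to the Table 1 failure definition: *study restoration repaired or replaced since treatment*. Keep that status at 12 months in the primary intention-to-treat comparison.
2. Report visit-status results (Table 1 as it now stands) and restoration quality alongside.
3. Record the date and reason of any retreatment.
4. State in the Sample size section that retreated teeth are outcome failures, not dropouts.

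The cost is one line in Table 1, a sentence each in the sample size and analysis sections, and one record field. The downside is that reported success rates may be lower. The change concerns only how the event is scored; it alters no rule on when or how a tooth is retreated.
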